5.3 Withdrawal Visit

For a variety of reasons, subjects may decide to withdraw from the study, or the PI may decide to terminate a subject's participation regardless of whether the subject wishes to continue participating. Withdrawal visit will consist in one day and the schedule of procedures will be the same as in Intermediate Visit 1. If the participant refuses to come to Center for Brain Health, the clinician will perform a clinical interview over the phone.

6 Study Procedures/Evaluations

6.1 Procedures/Evaluations

Clinical evaluation: all subjects will perform a standardized clinical evaluation (UDS 3.0) given to all participants seen at the NYU ADC. The purpose of this clinical evaluation is to establish that subjects are cognitively normal, identify concurrent medications that may act as confounders (*e.g.*, benzodiazepines, trazodone, suvorexant), increase reproducibility of the clinical evaluation, and facilitate collaborative research with NACC (see *Resource Sharing Plan*). Depressive symptoms will be measured using the Geriatric Depression Scale (GDS)^{212;213}. We will add information about: health insurance, annual household income, perceived discrimination (Index of Race-Related Stress [IRRS]-Brief Version B²¹⁴), the Weinstein Noise Sensitivity Scale (WNSS)²¹⁵, the Perceived Stress Scale (PSS)²¹⁶ and the SF36 health behaviors survey²¹⁷ to control for environmental, health and psychosocial factors that might disrupt sleep. In addition, all subjects will undergo complete fasting blood tests (CBC with differential and platelet count, highly sensitive CRP, ESR, total T₃ and T₄^{*}, lipid profile, RPR^{*}, comprehensive metabolic profile with insulin, folate^{*}, homocysteine^{*}, and vitamin B₁₂^{*}, SMA-18, HbA_{1c}, hemogram)). Subjects will then complete the WHICAP battery and the AMNART test⁴. The tests comprising this neuropsychological battery were chosen because unlike the UDS 3.0, they have race-specific norms⁵. We will construct three composite scores for general cognition, memory, and executive function from factor analyses. We will use total recall, delayed recall, and delayed recognition from the Buschke Selective Reminding Test²¹⁸ to construct the memory composite. The executive functioning composite will be created using the Color Trail-Making Test (A and B)²¹⁹, WAIS-R (Wechsler Adult Intelligence Scale-Revised), Similarities, Identities/Oddities subtest of the Mattis Dementia Rating Scale²²⁰, two cancellation tasks and semantic fluency for animals²²¹. All of the above variables, together with phonemic fluency²²¹, the 15-item Boston Naming Test²²², repetition task (high-frequency phrases of the Boston Diagnostic Aphasia Examination[BDAE]²²³; and a comprehension task, will contribute to the composite for general cognition. Means and standard deviations (SD) will be calculated from baseline scores for non-demented WHICAP subjects controlling for age, race and years of education using robust norms. Z-scores for each of the cognitive measures will be averaged to create a composite z-score for each of the three domains. Only subjects diagnosed as cognitively normal with a z-score >-1.25 SD of the mean in general cognition will be invited to participate. The time to complete the WHICAP test battery will range from 45-90 min. On visit 2, prior to the PET/MR scan, subjects will complete the UDS 3.0 cognitive evaluation to facilitate collaborative research with NACC.

Ambulatory home monitoring for OSA followed by actigraphy:

Subjects will be asked to monitor their sleep using sleep logs during one week. On the first night, OSA will be monitored using a WatchPAT (*Itamar Medical, Tel Aviv, Israel*) (Figure 8). We have experience using WatchPAT in AAs with very low failure rate (less than 1%). This self-applied device measures peripheral arterial volume changes using a finger-mounted plethysmograph. The information is collated

CONFIDENTIAL

This material is the property of the NYU School of Medicine and Langone Medical Center. Do not disclose or use except as authorized in writing by the study sponsor

with pulse oximetry and is further analyzed using an automated algorithm. This algorithm associates arousals with measurement of O₂Sat to determine respiratory effort-related arousals showing excellent sensitivity and specificity for identification of OSA, defined as AHI4% \geq 5 on full NPSG²²⁴. After automated analysis, all raw data and results are reviewed by [name]. Only subjects with an AHI4% $<$ 15 and AHI4% $>$ 5 with Epworth $<$ 10 will be invited to participate. Those cases with suspicion of OSA will be reviewed by [name] and [name]. If OSA is confirmed, they will be excluded and referred to a sleep specialist. Actigraphs (AMI, Ardsley, NY) (Figure 9) with off-wrist detection and a sleep diary will be provided to the subjects to use for the 7 days following the use of the WatchPAT. The purpose will be to record the sleep-wake cycle and provide estimates of total sleep time (TST) in the home. Actigraph will also provide bedtimes and wake times for NPSG N1-N2 in accordance with their usual sleep habits.

Figure 8.
WatchPAT

Figure 9. Actigraph

Measurement of Slow Wave Sleep (SWS) characteristics using NPSG:

Each in-lab NPSG will record sleep as recommended by the AASM²²⁵ as described in our previous work¹⁵⁶. Electrode attachment will be performed between 8-9 PM. Subjects will be then asked to sit quietly and/or read until lights out at their habitual bedtime. NPSG N1 will be for habituation, N2 will be for data collection. Arousal index (AI), sleep staging, TST, sleep efficiency and wake after sleep onset (WASO) during NPSG will be scored by one trained technologist blinded to PET data using standard AASM criteria²²⁵. Participants will go home between N1-2 provided that they wear the actigraph with off-wrist detection, avoid naps or exercise and track their meals. SWS will be scored visually as: 1) TST in SWS in min. (SWS duration); and, 2) %TST spent in SWS (%SWS). SWS measurements will be measured in N2. In addition, we will include: 1) slow wave activity (SWA): absolute SWA (defined as power between 0.5-4.0 Hz during NREM), relative SWA (SWA divided by power across all 0.4-50 Hz). NREM cycles will be defined as stages NREM2-3 of \geq 15 min. terminated by REM or wakefulness of \geq 5 min. Delta power will be averaged relative to the number of epochs. 2) SWS continuity: bouts of SWS will be defined as the duration of consecutive 30 sec. epochs of sleep scored as SWS, terminated by one or more epochs scored as another stage as described in our previous work^{226;227}.

Sleep-dependent Neuropsychological Tests:

On NPSG N2, participants will be trained in our published 3-D virtual maze spatial navigational test (see Figure 10)^{141;156}. Navigational memory represents a good model to study the effects of sleep-dependent memory consolidation. Rodent studies show that patterns of firing in hippocampal place cells during wake are replayed both in REM²²⁸ and NREM²²⁹ sleep. Behaviorally, sharp-wave ripple suppression impairs performance on a radial arm maze,²³⁰ while REM suppression impairs memory in the radial arm maze²³¹ and in the Morris water maze²³². In humans, overnight sleep enhances virtual maze navigation performance^{233;234}, while we have shown that maze completion time (CT) is attenuated after REM disruption¹⁷⁶ and is correlated with SWA in elderly subjects¹⁸⁸. Subjects will experience two different mazes at baseline and at the 2.5-year follow-up, and mazes will be counterbalanced across subjects for which maze is experienced first. Both mazes have been designed such that optimal CT is equivalent assuming perfect knowledge of the maze layout. Maze performance will be expressed as % change across sleep in maze CT compared to baseline CT before sleep. We have chosen a maze over a word-pair test^{105;235;236} because: 1) it taxes the hippocampus (more than a word-pair tasks would); 2) it's ecologically relevant to AD (*i.e.* spatial disorientation is one of the early clinical AD-symptoms); and 3) there are equivalent rodent models that lend insight into the underlying electrophysiological mechanisms (*i.e.* sharp-wave ripples, which cannot be captured with surface EEG).

Figure 10. Bird's eye view of virtual maze

PiB PET and MRI scans:

On visit 4, baseline and follow-up subjects will receive a single dose of 11.12 mCi PiB and perform a dynamic 60 min amyloid PiB PET-MR scan 35 min after injection.. The radioactive drug (PiB) shall meet appropriate chemical, pharmaceutical, and radionuclidic standards. The dose will be radioassayed proper to administration to ensure dosimetry data is correct. Further, the mass of the PiB is not expected to produce a pharmacologic response. PET/MR scans will be performed on an integrated 3T PET/MR

CONFIDENTIAL

(Siemens Biograph mMR, software Syngo MR B18P). For anatomic coregistration, a sagittal 3-D MPRAGE sequence will be performed (208 slices, 1mm isotropic voxels). Attenuation correction will be performed using a Dixon μ -map with a superimposed bone compartment and linear AC developed at NYU²³⁷. Modifying the linear AC value and superimposing a model-based bone compartment reduces the whole-brain SUV estimation bias of Dixon-based PET/MR AC by 95% compared with reference PET/CT AC ($p < .05$), resulting in a residual -0.3% SUV mean bias²³⁷. Ultrashort echo time (UTE) will also be acquired and combined to the Dixon μ -map to incorporate the bone tissue²³⁸. Simultaneous PET-MR acquisition eliminates the need of registering the PiB images to MNI. Instead, we will use the MPRAGE for registration, which offers a fine volumetric resolution and high contrast ratio required to precisely differentiate between GM and WM. For each patient, the MPRAGE image will be automatically segmented into, neocortical and cerebellar hemisphere GM regions of interest (ROIs) using *FreeSurfer*. These GM neocortical ROIs will be collapsed to yield four large volume-weighted ROIs that span prefrontal, lateral temporal, parietal cortex and anterior/posterior cingulate gyrus cortices (as described in²³⁹). An AD_{PiB} mask index will be the primary variable of interest in this study, derived by averaging these mean SUV values to a reference region containing the supratentorial WM and whole cerebellum. PiB+ will be defined as a AD_{PiB} mask ≥ 1.4 . The combined region will be used to calculate longitudinal estimates of change in PiB uptake.

Images for exclusion and structural brain measurements of middle prefrontal cortex (mPFC). Along with the PET acquisition we will acquire several sets of images intended to screen for brain disease, stroke or extensive white matter lesions. We will use a thin slice 3D sagittal T1 MPRAGE sequence. Parameters are: TR 2100 ms; TE 4.37 ms; TI 900 ms; flip angle 8° ; matrix 240 (read) x 256 (phase) x 208 (partitions); FOV 256 (read) x 192 (phase) x 240 (partitions) mm; iPAT 2; voxel size 1.0x1.0x1.0 mm; NEX 1; acquisition time 4.35'. Whole brain and cortical volumes: automatic brain segmentation, cortical surface reconstruction and parcellation will be performed using *FreeSurfer* (surfer.nmr.mgh.harvard.edu). Segmentations will undergo qualitative reviews and volumes will be residualized to intracranial volume (ICV)¹⁶⁹.

Fluid-attenuated inversion recovery (FLAIR): We will obtain complete brain coverage using 3D sagittal FLAIR SPACE sequences to quantify white matter lesions (WML). Parameters are: TR 6000 ms; TE 325 ms; TI 2100 ms; matrix 256 (read) x 248 (phase) x 176 (partitions); FOV 256 (read) x 248 (phase) x 176 (partitions) mm; iPAT 2; voxel size 1.0x1.0x1.0 mm; NEX 1; acquisition time 2.56'. WML volume (mL) is considered a surrogate marker of small vessel disease.²⁴⁰ It will be obtained using an semi-automatic approach based on hyperintense ($\geq \text{mean} + 2.5\text{SD}$) voxels in WM with our locally developed software *FireVoxel*^{241;242} (files.nyu.edu/hr18/public). WML volume will be subdivided into periventricular (PWML) and deep (DWML).

Diffusion Kurtosis Imaging (DKI) is an extension of diffusion tensor imaging (DTI)²⁴³ that provides the information obtained from DTI, plus additional non-Gaussian diffusion parameters,²⁴⁴ as well as new WM tract integrity (WMTI) metrics^{245;246} that are specific to underlying pathology: (a) axonal water fraction (*marker of axonal density*); (b) D_{axon} , diffusivity inside the axons (*marker of axonal injury*); and (c) $D_{e||}$ and $D_{e\perp}$, extra-axonal axial and radial diffusivity (*markers of extracellular inflammation, gliosis and demyelination*). We will use an optimized protocol in terms of number of shells (b-values) and encoding directions, providing the best coverage of q-space for diffusion and kurtosis tensors estimation within a short acquisition time (~ 7 min). The protocol can be summarized as follows: TR 8200 ms; TE 96 ms; b=0 (4 averages), b=250 (6 directions), b=1000 (20 directions), b=2000 (30 directions), s/mm², b=0 with reversed phase encoding direction (1 average); 50 axial slices; FOV 230 (read) x 230 (phase) mm²; voxel size 2.5x2.5x2.5 mm³. The DKI data will be used to derive parametric maps of DTI and DKI, followed by derivation of WMTI maps using our in-house developed processing pipeline (github.com/NYU-DiffusionMRI/Diffusion-Kurtosis-Imaging). Next, all maps will be transformed into standard space using FMRIB's Software Library. Mean values will then be extracted for each metric to assess the microstructural WM damage beyond lesions visible on FLAIR.

Individual Genetic Ancestry Estimation

Allele frequencies will be ascertained from Utah residents with Northern and Western European ancestry and West African (Yoruban from Nigeria) samples available in the HapMap database. Individual % African ancestry (%AF) estimates from 0-100 will be computed using a maximum likelihood method for inferring individual admixture²⁴⁷. Briefly, an algorithm is used to compute the probability of observing a marker genotype given ancestral allele frequencies at a locus. Summing over the logs of individual locus probabilities combines information across multiple loci. The admixture proportion that maximizes the

CONFIDENTIAL

probability of obtaining the observed genotype is the maximum likelihood estimate of ancestry for the individual^{199;248}.

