Brief Summary	African-Americans (AAs) have an increased prevalence of both Alzheimer's disease (AD) and vascular risk factors for AD such as diabetes and hypertension when compared to whites. However, in a recent community based study of non-demented elderly, black race was associated with higher amyloid burden after adjusting for vascular risk factors, suggesting the presence of additional physiological differences on AD-risk by race in the early stages of the disease. The purpose of this study is to test whether poor slow wave sleep (SWS) quantity (SWS duration) and quality (slow wave activity, SWA) is one of these physiological factors. To test these hypotheses, we will perform community outreach in barbershops, churches and senior centers in Brooklyn and other NYC boroughs with which we have created substantial ties in recent years. In consultation with community stakeholders, we will recruit 150 cognitively normal AA elderly (age 60-75) and 60 age, sex, BMI, income and education matched non-Hispanic whites from the same geographical areas. We will first perform a medical and cognitive evaluation (Visit 1). Participants will then undergo 2 nights of home sleep monitoring using an unattended device to exclude OSA, followed by 7 days of actigraphy with a sleep log to record sleep duration. Both devices will be returned by mail. Subjects with reported total sleep time (TST) between 5 and 10 hours and absence of moderate to severe OSA will be invited to perform a 2-night nocturnal polysomnography (NPSG) (Nights 1-2) and a PiB-PET MR scan (Visit 2).
Objectives	Objective 1: To test if African ancestry (%AF) is associated with short SWS duration and poor SWA in older AAs. Objective 2: To test the effect of race and its interaction with baseline short SWS duration/poor SWA on longitudinal amyloid deposition. Objective 3: To test the effect of race and baseline poor SWA on cognition. Secondary Objective 2.1: To test whether loss of sleep-dependent spatial navigational memory at baseline is a predictor of cognitive decline.
Methodology	30-36 month longitudinal study
Endpoint	Primary endpoint is longitudinal increase in amyloid deposition
Study Duration	5 years
Participant Duration	30-36 months

CONFIDENTIAL

[figure not shown]
This material is the property of the NYU School of Medicine and Langone Medical Center. Do not disclose or use except as authorized in writing by the study sponsor

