3.2 Secondary Objectives (if applicable)

Secondary Objective : **Exploratory:** we will test whether loss of sleep-dependent spatial navigational memory at baseline is a predictor of cognitive decline at follow-up. A **linked objective** is to identify how the relationship between SWS/SWA and the rate of change in PiB uptake might be confounded by mPFC atrophy (for measures of SWS) and DWML volumes and DKI (for measures of PiB uptake).

4 Study Enrollment and Withdrawal

Subjects:

210 cognitively normal, ages 60-75, self-identified as African-American (150) or non-Hispanic white

CONFIDENTIAL

This material is the property of the NYU School of Medicine and Langone Medical Center. Do not disclose or use except as authorized in writing by the study sponsor

(60), Clinical Dementia Rating (CDR) of 0, ≥ -1.25 in global cognition z-scores from the WHICAP battery adjusted for race and education, English speakers, and with enough literacy to provide voluntary consent will be invited to participate.

Exclusion criteria at enrollment will be: intention to move from NYC within the same year, irregular sleep-wake cycles defined as ‘ ≥ 3 sleep episodes per 24-hr period’ or ‘day to day irregularity greater than 90 min. based on actigraphy, less than 5 or more than 10 hours of TST; OSA (defined as $AHI_4\% > 15$ and $AHI_4\% > 5$ with $Epworth \geq 10$); neurodegenerative disorders, history of early onset familial AD; insulin dependent diabetes; bipolar disorder, schizophrenia, intellectual disability or substance abuse; non-controlled pulmonary or cardiac diseases; brain tumors; stroke; head trauma and hydrocephalus.

Lifelong depression and anxiety will be allowed as long as there has been no active depressive episode within the last two years. Current use of any sedative/hypnotics or stimulants, gabapentin, pregabalin, tricyclic antidepressants, and trazodone or other psychoactive medications that may alter SWS. Stable (3 months or longer) use of antidepressants will be allowed. Caribbean or African-born blacks or subjects that don't fulfill inclusion criteria but express interest will be offered participation in similar NYU NIH-funded studies on sleep or normal aging.

Study Enrollment:

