9.1 Study Hypotheses

1. Hypothesis 1.1: poor SWS characteristics (short SWS duration, low %SWS, low relative SWA, low SWS continuity and high AI) at baseline will be associated with high %AF. Hypothesis 1.2: psychosocial factors (*e.g.* perceived discrimination) will partially moderate the above relationships.
2. Hypothesis 2.1: race will be associated with longitudinal increases in the annual rate of AD_{PiB}mask change. Hypothesis 2.2: the effect of race in terms of longitudinal increases in AD_{PiB}mask will be partially explained by poor relative SWA at baseline.
3. Hypothesis 3.1: race will be associated with longitudinal changes in global cognition, memory, executive function and sleep-dependent spatial navigational memory. Hypothesis 3.2: the association of race in terms of cognitive decline will be partially explained by poor relative SWA at baseline. Exploratory Hypothesis: absence of improvement in sleep dependent memory consolidation at baseline will be associated with longitudinal decreases in global cognition, memory and executive function.

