linear regression, with rate of change of AD_{PiB}mask as the dependent variable and race as independent, adjusting for the matching factors: age, sex, BMI, education and annual income (block 1); ApoE4 and ABCA7 (block 2); DWML volumes, DKI indices and mPFC volume (block 3); and SWS characteristic (*e.g.* relative SWA) (block 4). Other covariates (*e.g.*, psychosocial) will be included in the final models if significantly different between AAs and whites as indicated by unequal variance t tests. Although we anticipate that relative SWA will be the best predictor of longitudinal change in AD_{PiB}mask, the best fitting model will be then replicated with each of the other SWS characteristics not listed before. On a final step, we will test whether the effect of SWS on amyloid deposition is different (*i.e.*, stronger) among AAs. The model would include AD_{PiB}mask change, the binary indicator of race (AA=1 *vs.* white=0) and SWA as described in H1.2. If the interaction is significant, it will imply that the effect of SWA on amyloid varies as a function of race. The sign of the estimated coefficient for this term would indicate whether SWA has a significantly stronger or weaker effect among AA. Exploratory Hypothesis: cognitive z-score change in subjects that show improvement in maze CT will be compared with those that don't show improvement using ANCOVA controlling for age, sex, BMI, race, education and ApoE4 status.

- **Post-hoc analyses**: a subset of *post-hoc* analyses will be performed by controlling by PiB levels at baseline and by splitting the sample into PiB+ and PiB- at baseline and performing a separate analysis for each subset. Stratified analyses will also be performed for men and women, as well as for AAs and whites. In addition, we will formally test the impact of PiB status (defined as PiB SUVR \geq 1.4) on the association of sleep measures with longitudinal increases in AD_{PiB}mask. Although we do not anticipate that sleep or SWS characteristics will change over the follow-up period, *post-hoc* analyses will be performed by assessing longitudinal changes in the sleep measures as correlates and predictors of longitudinal changes in the outcomes measures, using paired sample t-tests to assess the change in outcomes and sleep.

10 Source Documents and Access to Source Data/Documents

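### Aim 3 scores its three cognitive composites on race-adjusted norms and then tests race; depending on the norms, the contrast in cognitive change may be rescaled, and a common metric would avoid this

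*Combined protocol and SAP*

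**What the plan says.** Section 6.1 (clinical evaluation) chooses the WHICAP tests because, "unlike the UDS 3.0, they have race-specific norms". Reference means and SDs are taken from baseline scores of non-demented WHICAP participants, "controlling for age, race and years of education using robust norms". Then "Z-scores for each of the cognitive measures will be averaged to create a composite z-score for each of the three domains": general cognition, memory and executive function. The same kind of score serves eligibility. Section 4 (Subjects) sets a cut of -1.25 "in global cognition z-scores from the WHICAP battery adjusted for race and education".

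Hypothesis 3.1 in section 9.1 is that "race will be associated with longitudinal changes in global cognition, memory, executive function and sleep-dependent spatial navigational memory". Hypothesis 3.2 asks whether baseline relative slow wave activity explains part of that association. The Protocol Summary states the objective more loosely: "To test the effect of race and baseline poor SWA on cognition".

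Section 9.3 groups hypotheses 2 and 3 but writes the regression out with amyloid change as the dependent variable. The only cognitive scale it names is in the exploratory hypothesis: "cognitive z-score change in subjects that show improvement in maze CT". No un-normed or common-metric cognitive score is defined. The fourth outcome of hypothesis 3.1 is on a different scale: "Maze performance will be expressed as % change across sleep in maze CT compared to baseline CT before sleep".

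**The concern.** Race is the exposure in hypotheses 3.1 and 3.2, and it also enters the norms that set the scale of three of the four outcomes. Race norms have a clear purpose when deciding whether a person is cognitively normal. In a comparison between races they can change the quantity being estimated.

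For a change score the issue is narrower than for a level. An additive race mean is subtracted at both visits and drops out. Two routes remain:

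- **Norm SDs that differ by race.** The same raw decline is divided by different numbers in the two groups.
- **Age norms that advance between visits with race-specific slopes.** A race-specific expected ageing decline is then subtracted from the follow-up score.

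Section 6.1 refers to race-specific norms, to SDs as well as means, and to age. It does not say whether the SDs or the age terms differ by race, or whether follow-up is scored at baseline age or current age. If either route is active, the test of hypothesis 3.1 is distorted. The distortion carries into the %AF coding of race and into hypothesis 3.2.

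**Working it through.** **The plan's own figure.** Section 9.2 gives 80% power for a sleep measure explaining 3% of the variance in change, after covariates explaining 25%, with 200 complete participants. With f² = 0.03/(1 − 0.25 − 0.03) = 0.0417 and noncentrality 200 × 0.0417 = 8.3, power is 0.82, so the figure reproduces. It concerns the sleep term. The documents give no power figure for the race contrast in cognition.

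**Inputs.** From section 9.2: 150 AA and 60 white participants. From section 9.3: significance level 0.05. Assumed, because the documents do not give them: a two-sided test, SD of change 0.5, raw decline D of 0.2 to 0.4 over follow-up (both in white norm SDs), and k = AA norm SD / white norm SD.

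**Route 1, race-specific SDs.** With a fixed norm mean, z-change = raw change / norm SD. If both groups decline by D, the AA-minus-white contrast is −D/k + D = D(1 − 1/k), when it should be zero.

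| k | D = 0.2 | D = 0.3 | D = 0.4 |
|---|---|---|---|
| 1.0 | 0 | 0 | 0 |
| 1.1 | 0.018 | 0.027 | 0.036 |
| 1.2 | 0.033 | 0.050 | 0.067 |
| 1.3 | 0.046 | 0.069 | 0.092 |

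Simulated false-positive rates (20,000 trials per cell, n = 150/60):

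- k = 1.0: 5%.
- k = 1.1 to 1.3, Welch test: about 5.6% (k = 1.1, D = 0.2) to 24% (k = 1.3, D = 0.4); 10.6% at k = 1.2, D = 0.3.
- The same cells with a pooled-variance test, the analogue of ordinary linear regression: 6.6 to 31%; 13% at k = 1.2, D = 0.3.
- Zero decline with the pooled test, where no mean shift is possible: already about 6 to 8%.

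The last line shows that part of the pooled-test inflation comes from the unequal variances that rescaling creates, and not from the shifted contrast. For k below 1 the sign reverses: k = 0.8 with D = 0.25 gives 0.25 × (1 − 1.25) = −0.0625 SD and about 12% rejection (unequal-variance normal approximation, n = 143/57).

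**Power.** Take white decline 0.30 and AA decline 0.52, a true gap of 0.22.

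- Common metric: standard error 0.5 × √(1/150 + 1/60) = 0.076; 0.22/0.076 = 2.9; power about 81%.
- k = 1.2: the contrast is 0.52/1.2 − 0.30 = 0.133; the standard error is 0.5 × √(1/(1.44 × 150) + 1/60) = 0.073; the ratio is 1.8; power is about 44% (Welch) to 51% (pooled).

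**Full erasure through the SD.** This needs k equal to the ratio of the two declines. For a gap of 0.22 SD, k = 0.469/0.25 = 1.9 if white decline is 0.25, and 0.319/0.10 = 3.2 if it is 0.10. The most extreme case examined (SD of change 0.3, white decline 0.5, gap 0.132) needs 0.632/0.5 = 1.26.

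**Route 2, race-specific age slopes with age updated at follow-up** (n = 143/57, 2.5 years, SD of change 0.5). A true gap of 0.22 SD that matches the difference in norm slopes falls to 0.00, with 5% rejection. Equal decline with slopes differing by 0.03 SD per year creates 0.03 × 2.5 = 0.075 SD, with 16% rejection.

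**No active route.** With an additive race mean, one SD and common age slopes, the change contrast is intact: 5.0% false positives and 79% power for a gap of 0.22 SD (n = 143/57).

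**The case against.** The strongest reply is that the harm depends on a fact the documents leave open. Controlling for race also describes a regression-based norm with a single SD; z-change is then raw change over a constant and nothing happens. The norms are said to come from baseline scores, and no sentence says that follow-up is re-scored at current age. The choice was also deliberate: section 3.1 names poor validity of cognitive tests in African Americans as a problem this aim must meet. All of this stands. It makes the distortion conditional, but the stated scoring rule still uses the exposure under test, and no alternative score is defined.

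Three stronger readings are tempting and should be resisted:

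- **That race norming cancels the race effect outright.** This would hold for a comparison of levels: a raw baseline gap of 0.4 SD, with 72% power un-normed, becomes zero. The Summary's wording could suggest such a comparison, but hypothesis 3.1 concerns change, where a race mean drops out.
- **That the norms readily create or erase a difference.** At k = 1.2 a 20% faster AA decline does vanish (1.2D/1.2 = D). On declines of 0.2 to 0.4 SD that gap is only 0.04 to 0.08 SD, for which a perfect common metric has 8 to 18% power. Erasing a gap the study could detect usually needs k of about 1.5 or more.
- **That all of Aim 3 is affected.** The maze score is a raw percentage change, and the primary amyloid endpoint does not use these norms.

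**Conclusion.** The point holds in conditional form. Three of the four hypothesis 3.1 outcomes are defined on norms that include race, and the race contrast in their change is rescaled if the norm SDs differ by race or if age norms advance with race-specific slopes. The documents settle neither. Under the assumptions listed, the false-positive rate runs from 5% (equal norm SDs) to about 24% (Welch) or 31% (pooled variance) at an SD ratio of 1.3 with decline of 0.4 SD. Power for a 0.22 SD gap falls from about 81% to 44-51% at a ratio of 1.2. If decline in this cognitively normal cohort is small, the false-positive rate with a Welch test stays near nominal: 4.9 to 5.8% at decline 0.1. The main risk is distortion and lost power, with outright erasure confined to extreme cases. This is a worthwhile, inexpensive improvement to Aim 3 and does not bear on the primary endpoint.

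**What to change.** Keep the race- and education-normed z-score for the -1.25 eligibility cut. For the three Aim 3 composites, state in section 6.1 that each test is standardised at both visits with one common mean and SD not adjusted for race (for example, this cohort's pooled baseline) and then averaged into the composites. In section 9.3, write out the hypothesis 3 model: annual change in each composite as the dependent variable, with race, age, sex and education as regression terms (section 9.3 already lists age, sex and education in block 1 of the amyloid model). Report the race-normed version as a sensitivity analysis, stating which SDs and which age it uses.

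The contrast then becomes (AA change − white change)/common SD, whatever the form of the published norms.

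The cost is a short addition to each of the two sections and one extra analysis on the same raw data. The drawback is a metric tied to this sample, which is selected at -1.25 on the race-normed score and is 150/210 = 71% African American, and not to external norms.
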